## LIST OF ABBREVIATIONS

The following abbreviations and special terms are used in this Statistical Analysis Plan (SAP).

---

Abbreviation or special term	Explanation
CRC	Colorectal cancer
CRCRAT	Colorectal Cancer Risk Assessment Tool
FOBT	Fecal occult blood testing
FIT	Fecal immunochemical test
ITT	Intention-to-treat
SAP	Statistical Analysis Plan

---

## 1. BACKGROUND

Colorectal cancer (CRC) is the third most commonly diagnosed cancer among men and women in the United States and the third leading cause of cancer death. Although CRC carries significant morbidity and mortality, the 5-year survival is 90% when detected at a localized stage. Unfortunately, given that CRC screening is still underutilized, less than half of colorectal cancers are diagnosed at this localized stage. According to the data from the National Health Interview Survey (NHIS), only 58.3% of U.S. men and women aged 50-75 have undergone CRC screening using one of the following approved methods: colonoscopy, sigmoidoscopy, fecal occult blood testing (FOBT), fecal immunochemical test (FIT), double contrast enema, CT colonography, and stool DNA test. Numerous factors have been associated with suboptimal screening rates. These factors can be categorized into a non-modifiable factors (age, ethnicity, gender, educational level, health insurance, socioeconomic status) and modifiable factors (knowledge about CRC and screening, attitudes toward screening, and perception of risk for developing CRC). Modifiable factors are of particular interest given their susceptibility to change. More specifically, risk perception, or perceived susceptibility, as defined by the Health Belief Model, refers to an individual's subjective assessment of risk of developing a given health problem. Studies have shown that high-risk perception of developing CRC correlates with higher screening uptake. Similarly, underestimation of personal CRC risk is associated with lower screening uptake.

The National Cancer Institute (NCI) Colorectal Cancer Risk Assessment Tool (CRCRAT) is a validated online tool available to the general public, which estimates an individual's short-term and lifetime risk of developing colorectal cancer. The goal of this study is to determine if providing subjects with their personalized colorectal cancer risk will influence colorectal cancer screening behavior and intent. If the study leads to an increase in colorectal cancer screening rates in the group of subjects receiving this information as compared to a group that does not receive this information, then the investigators will propose that primary care clinics consider adopting the Colorectal Cancer Risk Assessment Tool into their practice in order to encourage colorectal cancer screening and prevention.

## 2. OBJECTIVES

### **Primary objective**

To determine whether knowledge of one's colorectal cancer risk (as approximated by the CRCRAT), as compared to not receiving this information, increases colorectal cancer screening rates in subjects who have never undergone screening test for colorectal cancer.

### **Secondary objective**

To determine whether knowledge of one's colorectal cancer risk (as approximated by the CRCRAT), as compared to not receiving this information, influences colorectal cancer screening intent and behavior in subjects who have never undergone screening test for colorectal cancer. This will be assessed by evaluating the following:

- 1) Colorectal cancer screening rates at 12 months
- 2) Colorectal cancer screening rates at 6 months
- 3) Change in screening intent at post-intervention as measured through stages in the Transtheoretical Model

### **3. TRIAL DESIGN**

This is a two-arm, open-label, randomized controlled study. Men and women between 50-75 years of age who have never undergone a screening test for colorectal cancer (and who have no known history of Ulcerative Colitis, Crohn's disease, Familial Adenomatous Polyposis, Lynch Syndrome, Personal history of colon cancer) will be randomized to the colorectal cancer risk information arm (CRCRAT arm) or to the no risk information arm (control arm). The study period for subjects will end approximately 12 months post-randomization.

Stanford Primary Care Clinic subjects who meet eligibility criteria will be identified through a pre-existing outreach list. A brief chart review will be conducted to ensure subjects meet particular inclusion/exclusion criteria. A letter will be sent to eligible subjects (along with the HIPAA authorization form), describing the research study and informing subjects that they will be contacted in the near future. Subjects will be provided with the option to "opt-out" of being contacted. Subjects will be contacted a few weeks later to give all subjects adequate time to respond.

Eligible subjects will be contacted using an approved telephone script to provide verbal consent for participation in the study. If a subject agrees to participate in the study, they will be immediately randomized, using blocked randomization, to either the CRCRAT or control arm. Both groups will then undergo a pre-intervention survey designed to assess attitudes towards colorectal cancer screening. Study interventions will be administered during this same telephone encounter. The control and intervention arms will both be read general information about colorectal cancer. The CRCRAT arm will then be guided through a series of questions from the NCI Colorectal Cancer Risk Assessment Tool in order to calculate their personalized risk of colorectal cancer. This personalized risk score will be recorded and subjects will be provided with the information on their risk scores. Immediately following these interventions, both arms will undergo a post-intervention survey, which again assesses attitudes towards colorectal cancer screening. Over the next 6 and 12 months, subjects' electronic medical records will be reviewed for colorectal cancer screening status. Subjects who were not screened, per their electronic medical record, will be contacted via phone or mail to see if they were screened elsewhere and/or assess their current screening intent. Subjects will be contacted no more than 3 total times for this research study.

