#### **8.2.2. Analysis methods**

The primary endpoint is the time to colorectal cancer screening. The date of the pre-intervention survey will be considered Day 0. The date of screening will be considered the date of the event. The date of follow-up phone call will be considered the date of event for subjects for whom a screening result is not recorded in the medical record and who self-report that screening was done. We will conduct a Cox proportional hazards regression model with study arm to evaluate our primary endpoint. In the per-protocol population, we will conduct similar analyses and include age group and gender as independent variables.

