## 8.3. Secondary endpoints

### 8.3.1. Definitions

#### 1) Colorectal cancer screening rates at 12 months

The secondary endpoint is whether a subject has had colorectal cancer screening at 12 months. Each subject will have an indicator of “Yes” or “No” for whether they were screened for colorectal cancer at 12 months. This will be determined by a review of subjects’ electronic medical records at 12 months post-randomization. Patient self-report on screening will be used for subjects for whom a screening result is not recorded in the EMR.

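### Never-screened status is checked at entry, as described, only by outreach list and chart, while self-reported outside tests count as outcomes with no requirement that they follow Day 0

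*Combined protocol and SAP*

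**What the plan says.** **Entry.** Section 3 (Trial Design) defines the population: "Men and women between 50-75 years of age who have never undergone a screening test for colorectal cancer". On sourcing it says that "subjects who meet eligibility criteria will be identified through a pre-existing outreach list", and then: "A brief chart review will be conducted to ensure subjects meet particular inclusion/exclusion criteria". The criteria covered by that review are not named. On the call: "If a subject agrees to participate in the study, they will be immediately randomized, using blocked randomization". Next: "Both groups will then undergo a pre-intervention survey designed to assess attitudes towards colorectal cancer screening". No question about earlier tests is mentioned before randomization.

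**Outcome.** Section 3 says that subjects with no screening in the medical record "will be contacted via phone or mail to see if they were screened elsewhere". Section 3.1 classifies subjects without a recorded result by self-report. Section 8.2.2 also counts self-report and adds a dating rule: "The date of follow-up phone call will be considered the date of event for subjects for whom a screening result is not recorded". Section 8.2.1 says the opposite for the same primary endpoint: no result in the record means not screened. Section 8.3.1 words the 12-month secondary endpoint as follows: "The secondary endpoint is whether a subject has had colorectal cancer screening at 12 months". It fills gaps in the record with self-report, and the 6-month endpoint is built the same way.

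**Afterwards.** Section 5 puts every randomized subject in the ITT set and defines the per-protocol set only by availability of 12-month data. Section 7.3 lists randomized but ineligible subjects as a deviation category to be summarized by arm, with no analysis rule attached.

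**The concern.** Entry and outcome are judged from different sources. The follow-up contact exists because the chart can miss tests done elsewhere. The plan allows for that gap when it measures the outcome, but describes nothing to close it at entry.

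Take a subject who had a colonoscopy at another institution some years ago that never reached the clinic record. The chart is blank, so the subject can be enrolled. At follow-up the subject may truthfully report having been screened elsewhere. No endpoint definition asks when. Under section 8.2.2 the event takes the date of the call, so the true date never enters the analysis and an old test looks like an on-study one.

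Two things are at stake: whether the analysed population is the never-screened one that the objectives name, and whether both arms carry events that happened before the intervention.

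**Working it through.** **1. Reproduce the plan's sample size.** Inputs from section 3.2: 50% screened by 6 months in control, 65% with the intervention, minimum follow-up 12 months, total 225. Sections 3.3 and 8.1.1 give 1:1 allocation and two-sided 0.05. Power is not stated; 80% is assumed.

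- Hazard ratio = ln(0.35)/ln(0.50) = 1.515, which the plan rounds to 1.5.
- Events (Schoenfeld) = 4 × (1.960 + 0.842)² / (ln 1.515)², rounded up = 183.
- Under constant hazards, 12-month rates are 1 − 0.50² = 0.75 and 1 − 0.35² = 0.8775, mean 0.81375.
- N = 183 / 0.81375 = 225, which matches the plan.

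**2. Add earlier outside tests.** Let q be the share in each arm with an unrecorded outside test before Day 0 that is later reported and counted. The documents give no value for q, so 5%, 10% and 20% are assumptions. As a simplification, each such subject is counted at the follow-up call and not before.

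- Observed rate in an arm = (1 − q) × p + q.
- Observed difference = (1 − q) × (p₁ − p₀). Example at q = 10%: 0.9 × 0.50 + 0.10 = 55% and 0.9 × 0.65 + 0.10 = 68.5%, a difference of 13.5 points instead of 15.

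**3. Effect on the Cox analysis.** Control hazard is ln 2/6 per month, hazard ratio 1.515, censoring at 12 months. For call-dating at 6 months there are two calculations: one large simulated sample (400,000 subjects) with power for 225 by normal approximation, and 4,000 simulated trials of 225. Where they differ, the range is shown. Call-dating at 12 months comes from the second only.

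| q (assumed) | 6-month rates, control vs CRCRAT | Difference (points) | HR, 6-month call | Power | HR, 12-month call | Power |
|---|---|---|---|---|---|---|
| 0 | 50% vs 65% | 15 | 1.51 | about 0.80 | 1.51 | 0.79 |
| 5% | 52.5% vs 66.75% | 14.25 | 1.49–1.50 | 0.77–0.78 | 1.49 | 0.77 |
| 10% | 55% vs 68.5% | 13.5 | 1.47–1.48 | 0.75 | 1.46 | 0.73 |
| 20% | 60% vs 72% | 12 | 1.44 | 0.70–0.71 | 1.41 | 0.65 |

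**4. Which endpoints.** The 6- and 12-month rates in 8.3.1 accept self-report without contradiction, so the point applies to them directly. For the primary endpoint it applies under 3.1 and 8.2.2 and not under 8.2.1.

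**The case against.** **Silence is not proof.** Contact uses an approved telephone script that is not in the documents, and the full survey is not there either. Either could ask about earlier tests. A reader might infer that the chart is the sole check and that old tests will be counted. The documents support only that no other check is described and that old tests can be counted.

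**The natural reading is on-study screening.** Section 3 introduces follow-up as covering the next 6 and 12 months, the primary endpoint is time from Day 0, and 8.3.1 ties record review to time since randomization. As to intent, this is fair. But no definition states the window and no test date is collected by which to apply it.

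**Section 8.2.1 would exclude the primary endpoint.** This stands, and limits the point as set out above.

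**The effect is modest and towards no difference.** This also stands. Randomization should balance earlier tests between arms, so a false benefit is not expected unless reporting differs by arm in this open-label trial.

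Four stronger inferences also fail:

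- *History surfaces more often in the CRCRAT arm because of its risk questions.* The tool's questions are not given.
- *Previously tested subjects cannot respond to the intervention.* Nothing says so; an earlier test does not rule out another.
- *A large part of all events would be spurious.* At the plan's rates and q = 10%, the 12-month control rate is 0.9 × 75% + 10% = 77.5%, so the share is 10/77.5, about 13%. A much larger share needs a larger q or rates that are not in the plan.
- *Excluding these subjects in a sensitivity analysis repairs the estimate.* Only subjects with no screening in the record are asked, and that status arises after randomization and is what the intervention aims to change. The exclusion could differ by arm.

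**Conclusion.** The point holds as a gap in the plan as written. Entry depends on a source that the plan itself treats as incomplete, the outcome adds a second source, and nothing requires a self-reported test to follow Day 0. The call-dating rule then hides an earlier test.

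The size is modest. Rates in both arms rise, the rate difference shrinks by the factor (1 − q), and at the plan's design rates power falls by about 5 percentage points for q = 10% with a 6-month call. The figures rest on an assumed q, equal in both arms, with every such subject reporting the test and being counted, on constant hazards, and on 80% design power. If the telephone script already asks about earlier tests, q could be much smaller, but the missing Day 0 rule would remain. This is an inexpensive improvement worth making, not a flaw that invalidates the trial.

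**What to change.** 1. **Before randomization**, ask in the telephone script whether the subject has ever had any of the listed tests anywhere (the list is already in Table 2, section 8.3.2). Do not randomize those who say yes. If the script already asks this, say so in section 3.
2. **At the existing follow-up contact**, ask the month and year of any self-reported test. In sections 3.1, 8.2.2 and 8.3.1, count it only if it was done after Day 0.
3. **Reconcile** 3.1 and 8.2.2 with 8.2.1 on whether self-report counts for the primary endpoint.
4. **Keep all randomized subjects in the ITT set.** A test before Day 0 is not an event. Report these subjects by arm under the section 7.3 deviation category, and do not rely on an analysis that excludes them.

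Both of the first two changes are needed. With the second alone, a previously tested subject with no test on study is correctly scored as unscreened but stays in the denominator, so the rate difference is still diluted.

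The cost is one question on the enrolment call, one at follow-up and short edits to the SAP. No extra contact is needed, so the limit of three contacts in section 3 is kept. A few candidates will be screened out, and recall of old tests is imperfect, so some misclassification will remain.

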### **3.3 Randomization and blinding**

Subjects will be randomized 1:1 using block randomization stratified by gender (male/female) and age group (under 60 years old or 60 years old and over) to either the CRCRAT arm or control arm. The randomization scheme will be generated using the 'blockrand' package in R. The 'blockrand' function randomizes subjects to specified groups within sequential blocks; block sizes were randomly chosen from the set of 2, 4, 6, 8. The randomization scheme will be incorporated into REDCap in order to assign participants into the treatment groups. This is an open-label study with no blinding.

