#### 3) Change in screening intent at post-intervention as measured through stages in the Transtheoretical Model.

Screening intent will be measured through stages in the Transtheoretical Model.

Screening intent will be coded as a multi-level categorical variable: “pre-contemplation”, “contemplation” and “preparation” using two specific survey questions (see Table 1). Change in intention to screen for colorectal cancer will compare responses at pre- and post-intervention.

Table 1. Definition for screening intent endpoint

Endpoint	Coding

Change in intent to screen comparing 6months and 12 months to baseline
 
“How much do you agree or disagree: I am intending to have one of the following screening tests within the next 6 months?”
 
(Strongly Disagree, Somewhat Disagree, Somewhat Agree, Strongly Agree)
 
“Have you scheduled one of the above screening tests to be done within the next year?” (No, Yes)
	
As noted above:
 
Precontemplation (Strongly Disagree, Somewhat Disagree) = 0 (reference category)
 
Contemplation (Somewhat Agree, Strongly Agree) = 1
 
Preparation (scheduled a screening test) = 2
 
Did not answer = missing

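### Randomizing before the pre-intervention survey in an open-label call leaves the baseline intent answers unprotected from the caller's knowledge of the arm, and leaves anyone who exits in between without a stated Day 0

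*Combined protocol and SAP*

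**What the plan says.** All quotes are from the combined protocol and SAP.

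- **Order of the call (section 3, Trial Design).** After verbal consent, subjects are allocated: "they will be immediately randomized, using blocked randomization, to either the CRCRAT or control arm". The survey follows: "Both groups will then undergo a pre-intervention survey designed to assess attitudes towards colorectal cancer screening". Both arms then hear general information, the CRCRAT arm goes through the risk tool, and both arms take the post-intervention survey. It is all one call: "Study interventions will be administered during this same telephone encounter".
- **Blinding and assignment (section 3.3).** "This is an open-label study with no blinding". The arm comes from REDCap: "The randomization scheme will be incorporated into REDCap in order to assign participants into the treatment groups". The strata are simple: "Subjects will be randomized 1:1 using block randomization stratified by gender (male/female) and age group".
- **Use of the survey (section 8.3.1, endpoint 3).** "Change in intention to screen for colorectal cancer will compare responses at pre- and post-intervention". Section 8.3.2 models intent with a multinomial logit random effects model containing arm, time (pre/post) and a subject effect. It also adds knowledge, fear and risk perception in separate models. Section 9 plans baseline analyses of the same answers.
- **Time origin (section 8.2.2).** "The date of the pre-intervention survey will be considered Day 0". Section 5 defines the ITT set as everyone randomized.

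**The concern.** A baseline measure is normally taken before allocation, so that neither the person asking nor the person answering can be influenced by the arm. Here the allocation exists before the first survey item is read, and the person who reads it goes on to deliver the arm-specific content. The items are subjective agree/disagree and likelihood questions asked by telephone, so tone, pace or prompting could differ by arm.

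Two things are at stake.

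1. The pre-intervention answer is one half of the change-in-intent endpoint. In the planned model it is a repeated outcome rather than a covariate fixed before randomization, so an arm-related difference in it can enter the estimated difference in change.
2. A subject who ends the call between allocation and survey has been randomized but has no baseline intent and no survey date. Such exits come after allocation, so they could differ by arm.

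**Working it through.** **Step 1. Sequence and concealment.** Section 3 gives the order as consent, randomization, pre-intervention survey, general information, CRCRAT (one arm), post-intervention survey. Section 3.3 gives no blinding, and REDCap returns the arm. No section says that the assignment stays hidden until the survey form is closed. It follows that the caller can know the arm during the survey. The documents do not say whether the caller looks at it then, or whether the subject is told.

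**Step 2. Is the order needed?** The strata are gender and age group. No survey answer is needed to randomize, and the plan gives no other reason for the order.

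**Step 3. Primary analysis.** Randomization and survey occur in one call, so the survey date equals the randomization date for everyone surveyed. The order therefore does not move Day 0 for them. What remains is the subject who is in the ITT set (section 5) but has no survey date (section 8.2.2). If 1% to 3% left at that point (an assumption), this would be 0.01 × 225 = 2.25 to 0.03 × 225 = 6.75, or about 2 to 7 subjects.

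**Step 4. Sample size.** The planned total is 225 (section 3.2). Power is not stated; 80%, two-sided 0.05 and no dropout are assumed here.

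- Hazard ratio: ln 0.35 / ln 0.50 = 1.515.
- Events (Schoenfeld): 4 × (1.960 + 0.842)² / (ln 1.515)² = 183 after rounding up.
- Event probability at 12 months, exponential times with a control median of 6 months: 0.750 and 0.8775, mean 0.814.
- N = 183 / 0.814 = 225.

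The planned figure reproduces. None of its inputs depends on the order of the survey and randomization, so the change proposed below leaves it at 225.

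**Step 5. What a baseline shift would do to the intent endpoint (illustration).** Assumptions, none from the documents: 50% intending to screen; a binary change score in place of the three-level model; no true effect; a shift in the baseline answers of one arm only, with nothing carried into the post-intervention answers. There are 225 / 2 = 112.5 subjects per arm.

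- Variance of change = 2 × 0.25 × (1 − r), where r is the pre/post correlation.
- SE of the arm difference = √(2 × variance / 112.5).
- Type I error = P(|Z + shift/SE| > 1.96).

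| r | Variance | SE | 3-point shift | 5-point shift |
|---|---|---|---|---|
| 0.5 | 0.25 | 0.067 | 7% | 12% |
| 0.7 | 0.15 | 0.052 | 9% | 16% |
| 0.9 | 0.05 | 0.030 | 17% | 39% |

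On the odds scale, lowering a 50% baseline by d in one arm gives a spurious ratio of odds ratios of (0.5 + d)/(0.5 − d): 0.52/0.48 = 1.08 for 2 points, 0.55/0.45 = 1.22 for 5 points and 0.60/0.40 = 1.50 for 10 points.

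**The case against.** **Knowledge of the arm is not shown.** A reader might infer that baseline intent is collected with the arm known to both parties. The documents do not say that. The described content is the same for both arms until the CRCRAT questions, which come after the survey and the general information. This stands: the supported claim is a risk of caller influence on fixed-response items and of differential exit, not demonstrated contamination.

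**The primary analysis is not biased by the order.** A reader might infer that a Day 0 set after randomization distorts the Cox analysis. It does not, because both steps fall in the same call. Nor need a subject without a survey be lost from the model. Section 5 keeps such subjects in the ITT set, sections 3 and 8.3.1 already count time from randomization, and section 8.1.2 undertakes to include partial data. This stands too: it is a gap in the definition, and a Day 0 set at randomization closes it without any reordering. That alone would not protect the survey answers.

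**Influence may cancel.** The same unblinded call contains the post-intervention survey. An influence that acts alike on both surveys would largely drop out of the change. This stands as a limit on the illustration, which assumes an effect at baseline only. It does not make the baseline protected.

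**The remedy is partial and not free.** The post-intervention survey stays unblinded, and section 3 refers to an approved telephone script, so a new sequence may need approval. Both points stand and are counted in the cost.

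**Conclusion.** The point holds as an avoidable design weakness of limited reach. The order of steps and the absence of blinding are explicit, and nothing in the plan conceals the arm from the caller during the baseline survey. The exposure is to the secondary change-in-intent endpoint and to the analyses that use baseline knowledge, fear and risk perception.

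The size of any bias cannot be estimated from the documents. The type I error figures of 7% to 39% rest on an assumed shift of 3 or 5 points at baseline only, an assumed 50% prevalence, correlations of 0.5 to 0.9 and a binary score. They show that a modest shift would matter if it occurred, not that one is likely.

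For the primary endpoint, the only consequence is the missing time origin for any randomized subject who leaves before the survey: about 2 to 7 of 225 if 1% to 3% do so, which is again an assumption.

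**What to change.** **Subjects not yet enrolled.** In section 3, change the sequence to: consent, pre-intervention survey, REDCap randomization, general information, CRCRAT if allocated, post-intervention survey. Let the REDCap randomization step open only once the survey form is complete. Bring section 8.2.2 into line by defining Day 0 as the randomization date, so that every ITT subject has a time origin.

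**Subjects already enrolled with randomization first.** Report baseline intent by arm, report the number who left between randomization and survey by arm, and state the order as a limitation. The Day 0 definition above can serve these subjects too.

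**Cost.** A minor revision of the telephone script and REDCap form, possibly with re-approval. The steps stay within the same call, with no further contact and no change to the 225. The post-intervention survey would still be conducted unblinded.
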